### **5.1.2. Safety and Tolerability**

Please refer to the Investigator's Brochure for a detailed discussion of safety findings for studies in healthy subjects, cancer, CKD, and PH patients with bardoxolone methyl.

#### **5.1.2.1. Fluid Overload**

Similar to endothelin receptor antagonists in certain patient populations, including bosentan in advanced congestive heart failure and avosentan in advanced CKD, bardoxolone methyl treatment was found to be associated with an increased risk for fluid overload and heart failure hospitalizations in the BEACON trial, which enrolled patients with Stage 4 CKD (eGFR 15 to 29 mL/min/1.73 m^2) and T2D. The overall increased risk for fluid overload and heart failure events with bardoxolone methyl appeared to be limited to up to four weeks after initiation of treatment. Elevated B-type natriuretic peptide (BNP) and prior hospitalization for heart failure were identified as risk factors that contributed to increased risk for these events. The increased risk for these events from bardoxolone methyl treatment had not been observed in six previous CKD studies, which were conducted mostly in patients with Stage 3b CKD (eGFR of 30 to 44 mL/min/1.73 m^2), patients with hepatic dysfunction, cancer patients, or healthy volunteers.

Review of admission notes and narrative descriptions for heart failure hospitalizations in BEACON indicates that heart failure in bardoxolone methyl-treated patients was often preceded by rapid fluid weight gain (several kilograms within the first weeks of treatment initiation) and was not associated with acute renal decompensation or acutely reduced left ventricular contractility. Available data from BEACON and other studies suggest that bardoxolone methyl treatment can differentially affect hemodynamic status according to the clinical condition of patients and likely promotes fluid retention in patients with more advanced renal dysfunction and other recognized risk factors associated with heart failure at baseline.

Risk mitigation procedures have been employed in subsequent trials to reduce the potential for bardoxolone methyl-induced fluid overload; these procedures excluded patients with the identified risk factors and ensured close monitoring for fluid retention within the first month of treatment.

#### **5.1.2.2. Aminotransferase and Gamma-glutamyl Transferase Elevations**

In clinical studies of bardoxolone methyl, almost all patients had increases of aminotransferase enzymes above baseline upon initiation of treatment, which followed a consistent pattern. These increases were not associated with elevations in bilirubin or other signs of liver toxicity. In BEACON, fewer hepatobiliary serious adverse events (SAEs) were observed in the bardoxolone methyl arm than in the placebo arm. The elevations begin immediately after initiation of treatment or an increase in dose; they peak approximately two to four weeks later. In most patients, aminotransferase elevations were mild, but approximately 4% to 11% of patients experienced an elevation greater than 3X the upper limit of normal (ULN). The elevations resolved to levels less than the ULN in most all patients with elevations, within two weeks after peak values while patients continued taking study drug.

Patients who experienced elevations to greater than 3X the ULN sometimes required additional time to resolve. While some patients have had elevations to above 3X the ULN, persistent

elevations to above 3X the ULN have not been observed, and the elevations did not recur once resolved, unless caused by other factors.

Bardoxolone methyl regulates gamma-glutamyl transferase (GGT), a known Nrf2 target gene protein. In clinical studies, low level GGT elevations during treatment were common, mild, and typically lasted longer than alanine/aspartate aminotransferase (ALT/AST) elevations. Bilirubin levels in patients experiencing aminotransferase or GGT elevations due to treatment with bardoxolone methyl either remained at baseline levels or decreased. The ALT, AST, and GGT elevations were generally self-limiting in patients who continued treatment with study drug.

#### **5.1.2.3. Muscle Spasms**

Muscle spasm was the most frequently reported adverse event (AE) in clinical trials of bardoxolone methyl in patients with CKD. The muscle spasms most often manifested in the first two months of treatment and resolved spontaneously or with empirical treatment. They occurred mostly at night, in the lower extremities, and were generally mild to moderate in severity. Muscle spasms may result from improved insulin sensitivity and glucose uptake in skeletal muscle cells. Increases in glucose uptake, as assessed by the hyperinsulinemic-euglycemic clamp procedure, were observed in response to bardoxolone methyl in a defined subset of patients enrolled in a Phase 2a study. To date, in those cases where serum creatinine kinase (CK) levels have been measured, no association has been observed between muscle spasms and elevated CK levels in patients treated with bardoxolone methyl. Clinical signs and laboratory findings associated with the reports of muscle spasms have not been consistent with muscle toxicity. Bardoxolone methyl subjects showed no increase in prominent laboratory findings associated with muscle toxicity, such as increased levels of serum markers, including creatinine, lactate dehydrogenase (LDH), blood urea nitrogen (BUN), uric acid, phosphorus, and potassium, which were monitored weekly during the first two months of a prior study (402-C-0804) when muscle spasms were most frequently reported.

Increases in the whole-body glucose disposal rate have been observed in mice treated with bardoxolone methyl, as well. Increased glucose uptake was observed in isolated calf muscles of the mice, but not in white adipose tissue ([Saha, 2010](#)).

#### **5.1.2.4. Weight Loss**

Decreases in weight and reports of anorexia/decreased appetite have been observed following treatment with bardoxolone methyl in patients with CKD. In studies of these patients, 17% of bardoxolone methyl patients reported AEs of weight decrease or decreased appetite (irrespective of relationship to treatment). Weight reduction was more pronounced in patients treated with bardoxolone methyl than in those given placebo.

Weight loss of approximately one kilogram per month was observed, with patients of higher body-mass index at baseline losing more weight (in absolute terms) than those of normal or moderately-elevated body-mass index ([Chertow, 2018](#)).

#### **5.1.2.5. Hypomagnesemia**

Hypomagnesemia was reported as an AE for 15.5% of patients with T2D CKD who received bardoxolone methyl. The AE of hypomagnesemia (of any reported relationship to study drug) was more frequently reported in bardoxolone methyl-treated patients than in patients given

placebo. The investigators considered almost all reported events to be mild. Additionally, patients treated with bardoxolone methyl had a greater decrease from baseline in serum magnesium levels than patients given placebo; the decrease was evident within 4 weeks and attenuated after 8 weeks of starting therapy. In bardoxolone methyl clinical studies performed to date, a post-hoc analysis identified no correlation between hypomagnesemia and either gastrointestinal AEs or cardiac AEs, including cardiac dysrhythmias and prolonged corrected QT interval (QTc). The 24-hour urine collections from the BEACON ambulatory blood pressure monitoring sub-study showed no increase in urinary magnesium levels, indicating that renal loss of magnesium did not account for the reductions in serum magnesium observed with bardoxolone methyl treatment in CKD patients. Notably, a thorough QT study that tested doses of bardoxolone methyl up to 80 mg, bardoxolone methyl showed no increase in the QT interval ([Chin, 2019](#)).

#### **5.1.2.6. Increases in Urinary Protein**

Increases in urinary albumin have been observed in some patients treated with bardoxolone methyl with chronic kidney disease. The increases are likely due to bardoxolone methyl's pharmacological modulation of tubular protein reabsorption and have not been associated with interstitial fibrosis or injury. In preclinical studies, bardoxolone methyl has been shown to downregulate the primary proteins involved in protein reabsorption in the proximal tubules: the megalin-cubilin complex ([Reisman, 2012](#)). Moreover, the magnitude of observed eGFR increases with bardoxolone methyl treatment is thought to reduce the residence time of protein in the proximal tubules, thereby reducing protein reuptake and increasing urinary protein levels.

Therefore, increased eGFR, together with decreased megalin expression, is thought to result in decreased fractional absorption of albumin and increased urinary excretion of albumin.

Consistent with bardoxolone methyl-mediated protection in preclinical models of protein-overload-induced nephropathy, these pharmacological effects are thought to reduce protein overload and secondary nephropathy caused by excessive albumin uptake and therefore are not associated with tissue injury and interstitial fibrosis ([Rossing, 2019](#)).

## **6. STUDY OBJECTIVES AND ENDPOINTS**

### **6.1. Study Objectives**

The study objectives are as follows:

#### **6.1.1. Primary Objectives**

- To assess the change from baseline in estimated glomerular filtration rate (eGFR) at Week 12.
- To assess the safety and tolerability of bardoxolone methyl.

#### **6.1.2. Secondary Objective**

- To characterize the eGFR response at Week 12 across different etiologies of Chronic Kidney Disease (CKD).

#### **6.1.3. Exploratory Objectives**

- To characterize change in eGFR during the off-treatment period.
- [REDACTED]

## **6.2. Study Endpoints**

### **6.2.1. Primary Efficacy Endpoint**

- eGFR change from baseline at Week 12.

### **6.2.2. Secondary Efficacy Endpoint**

- eGFR change from baseline at Week 12 by CKD etiology.

### **6.2.3. Exploratory Efficacy Endpoint**

- eGFR change from baseline at off-treatment Days 3, 7, 14, 21, 28, and 35.

### **6.2.4. Safety Endpoints**

- Laboratory results (clinical chemistry, hematology, urinalysis, and microscopy), vital sign measurements, electrocardiogram (ECG) results, weight, adverse events (AEs), and serious adverse events (SAEs).

### **6.2.5. Other Endpoint**

- [REDACTED]

## 7. INVESTIGATIONAL PLAN

### 7.1. Overall Study Design

This multi-center, randomized, double-blind, placebo-controlled, Phase 2 trial will study the safety, tolerability, and efficacy of bardoxolone methyl in qualified patients with CKD due to multiple etiologies at risk of rapid disease progression. Approximately 70 patients will be enrolled and randomized 1:1 to either bardoxolone methyl or placebo. Randomization will be stratified using the Kidney Disease: Improving Global Outcomes (KDIGO) CKD progression risk heat map (stratum 1 = yellow or orange; stratum 2 = red or dark red) (Section 19, Levin, 2014) based on screening eGFR and UACR using Randomization and Trial Supply Management (RTSM).

Patients with CKD secondary to varying etiologies will be enrolled from age 18-75 years with eGFR  $\geq 20$  to  $< 60$  mL/min/1.73 m^2, and other risk factors for rapid progression of kidney disease. Patients with glomerulonephritis requiring immunosuppressive treatment within 6 months or a history of rapidly progressive glomerulonephritis will be excluded. No single CKD etiology (hypertensive, diabetic, or other) may enroll approximately  $\geq 40\%$  in the trial.

The maximum target dose will be determined by baseline proteinuria status. Patients with baseline urine albumin to creatinine ratio (UACR)  $\leq 300$  mg/g will be titrated to a maximum dose of 20 mg, and patients with baseline UACR  $> 300$  mg/g will be titrated to a maximum dose of 30 mg. Qualified patients will be randomized 1:1 to receive either bardoxolone methyl or placebo once daily (preferably in the morning) throughout a 12-week dosing period. Patients will start with once-daily dosing at 5 mg and will dose-escalate to 10 mg at Week 2, to 20 mg at Week 4, and then to 30 mg at Week 6 (only if baseline UACR  $> 300$  mg/g), unless contraindicated clinically, which should be discussed with the medical monitor (Figure 1). Dose de-escalation is permitted during the study if indicated clinically, and subsequent dose re-escalation is also permitted to meet the dosing objective of the highest tolerated dose.

Patients in the study will follow the same visit and assessment schedule. Patients will be assessed during treatment at Day 1, Weeks 1, 2, 4, 6, 8, and 12 and by telephone contact on Days 3, 10, 21, 31, 35, and 45. Date of last dose and the end-of-treatment assessments mark the end of the treatment period. Patients will not receive study drug during a 5-week off-treatment period between Weeks 12 and 17 (Figure 1).

[figure not shown]
The off-treatment (OT) period includes 5 visits requiring various assessments to characterize eGFR from the time of study drug discontinuation through Day 35 off-treatment. Patients will be assessed on Day 3 OT, Day 7 OT, Day 14 OT, Day 21 OT, Day 28 OT, and Day 35 OT. The OT day corresponds to days after last dose. Day 1 OT is the first day after receiving the last dose. Any patient who permanently discontinues study treatment early will follow the same OT assessment schedule.

All patients, including patients who discontinue treatment early, should complete the end-of-study (EOS) visit 17 weeks after randomization.

All efforts should be made to follow all randomized patients for the full OT period of the trial, and the EOS visit (Week 17), including patients who discontinue drug early.

Final analysis of the primary efficacy endpoint will occur after all enrolled patients have completed their Week 17 visit (or have terminated from the trial).

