a If a patient permanently discontinues study drug early, the patient should return as soon as possible to complete EOT procedures (i.e., those outlined at the Week 12 visit). The OT visits should then be scheduled based on the date of the last dose of study drug. Following completion of the OT visits, the EOS visit will occur at Week 17. In this case, there will be both an OT Day 35 visit scheduled 35 days following the last dose of IP and an EOS visit scheduled approximately 17 weeks after Day 1/randomization.

b Total Screening period should not exceed 4 weeks.

c Day 1 is administration of the first dose. **On Day 1, all procedures must be performed before study drug administration.**

d Screening eligibility procedures do not need to be repeated on Day 1; however, a review of any changes in eligibility criteria should be evaluated prior to Day 1 procedures, and a urine pregnancy test should be performed for WOCBP.

e AE assessments on Day 1 should be performed following study drug administration.

f Weights should be taken at the same time each day and recorded in a patient diary. During the first eight weeks, weights will be recorded daily; weekly weights will be recorded from Week 8 through Week 12.

g Blood pressure for inclusion criteria eligibility can be taken at Screen A or Screen B. Blood pressure should not be collected at Screen B if Screen A values met eligibility criteria.

h Investigator should evaluate if a targeted physical exam is needed, based on any symptomatology reported to the study team.

i A serum pregnancy test will be performed at the Screen A visit for WOCBP or at any point in time if a pregnancy is suspected. All other pregnancy assessments will be urine pregnancy tests. Additional pregnancy assessments will be performed more frequently if required by local law or requested by local regulatory authorities or IRBs/ECs.

k Urine albumin to creatinine ratio will be measured by first morning void spot urine collection. Containers for the collection will be provided to the patient at the visit prior to the collection.

l Patients must not take study drug on the day of the Week 12 visit since PK will be drawn.

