#### **7.6.4. Week 12 (End of Treatment) Visit**

Week 12 is the final visit in the Treatment Period, and it marks the transition to the OT Period. Careful attention should be paid to ensure the visit is scheduled between Day 81 and Day 84, as outlined in [Table 4](#).

**Patients should be instructed to refrain from taking IP on the day of the Week 12 visit. The last dose of study drug should be the day prior to the Week 12 visit.**

If a patient permanently discontinues study drug early, please refer to Section [8.3](#).

Assessments to be completed at the Week 12/EOT Visit include the following:

- Review and record concomitant medications
- Review and record AEs
- Perform vital sign assessments (sitting blood pressure, pulse, heart rate, temperature, and weight)
- Collect/review weight and IP diary
- Perform 12 lead ECG at rest
- Perform a targeted physical examination, if needed
- Perform urine pregnancy test, if applicable
- Collect and review study drug

- Perform a buccal swab (cheek swab) for genetic testing (if not already collected)
- Collect blood and urine for clinical laboratory tests:
  - Clinical chemistry, including eGFR
  - BNP and NT-proBNP
  - Hemoglobin A1c
  - Hematology
  - Urinalysis and microscopy
  - Urine for UACR - first morning void specimen
  - Liver and Kidney Injury Biomarkers
  - C-Reactive Protein
  - PT/INR
- Collect blood for PK

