#### **7.6.5. Off-Treatment Period (OT Day 3 to OT Day 35)**

The OT Period includes 5 visits and includes various assessments to characterize eGFR from the time of drug discontinuation through Day 35 off-treatment. AEs and SAEs should continue to be collected during this period.

All visits in the OT Period should be scheduled based on the date of the Week 12/EOT visit.

If a patient permanently discontinues study drug early, please refer to Section 8.3.

The OT period must include the following assessments:

- Review and record prior concomitant medications
- Review and record AEs
- Collect blood for clinical chemistry, including eGFR
- Collect blood for PK

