**Table 2: Schedule of Assessments**

Assessments	Screening		Treatment Period												EOT	Off-Treatment Period (Based on Date of Last Dose)				EOS a	
	Screen A b	Screen B b	Day 1 c	Day 3 Day 3 ±2	Wk 1 Day 7 ±3	Day 10 Day 10 ±2	Wk 2 Day 14 ±3	Wk 3 Day 21 ±2	Wk 4 Day 28 ±3	Day 31 Day 31 ±2	Wk 5 Day 35 ±2	Wk 6 Day 42 ±3	Day 45 Day 45 ±2	Wk 8 Day 56 ±3	Wk 12 a Day 84 –3	OT Day 3 +1	OT Day 7 ±2	OT Day 14 ±3	OT Day 21 ±3	OT Day 28 ±3	OT Day 35 –3 Week 17
Visit Method	Clinic	Clinic	Clinic	Phone	Clinic	Phone	Clinic	Phone	Clinic	Phone	Clinic	Phone	Clinic	Clinic	Clinic	Clinic	Clinic	Clinic	Clinic	Clinic	
Informed consent	X																				
Inclusion/ exclusion	X		X d																		
Demographics and baseline disease characteristics	X																				
Medical history	X																				
Collect CKD etiology	X																				
Height	X																				
Prior and concomitant medications	X	X	X	X	X	X	X	X	X	X	X	X	X	X	X	X	X	X	X	X	
AE collection			X e	X	X	X	X	X	X	X	X	X	X	X	X	X	X	X	X	X	
Weight in clinic	X		X		X		X		X		X		X		X						X
Weight at home f			X	X	X	X	X	X	X	X	X	X	X	X	X	X					
Dispense weight and IP diary			X				X		X		X		X		X						
Collect/review weight and IP diary				X	X	X	X	X	X	X	X	X	X	X	X						
ECG	X																				X
Vital sign measurements	X g		X		X		X		X		X		X		X						X
Physical exam	X																				X
Targeted physical exam h			X		X		X		X		X		X		X						
Pregnancy test for WOCBP i	X	X	X		X		X		X		X		X		X						X
Study drug administration										X											
Dispense study drug			X				X		X		X		X		X						
Collect/review study drug							X		X		X		X		X						
			X																		
Clinical chemistry (incl. eGFR)	X	X	X	X	X	X	X	X	X	X	X	X	X	X	X	X	X	X	X	X	
BNP and NT-proBNP	X		X		X		X		X		X		X		X						X
Hemoglobin A1c	X																				
Hematology	X		X		X		X		X		X		X		X						X
Urinalysis and microscopy	X		X		X		X		X		X		X		X						X
Urine collection for UACR k		X							X				X		X						X
PK samples l													X		X		X		X		X

Assessments	Screening		Treatment Period												EOT	Off-Treatment Period (Based on Date of Last Dose)			EOS a

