**Table 4: Analysis Visits for Off-Treatment assessments**

Off-Treatment Analysis Visit	Label	Target Study Day (days after last dose)	Analysis Window
3	Off Treatment Day 3 b	3	2 ≤ days after last dose ≤ 4
7	Off Treatment Day 7 b	7	5 ≤ days after last dose ≤ 10
14	Off Treatment Day 14 b	14	11 ≤ days after last dose ≤ 17
21	Off Treatment Day 21 b	21	18 ≤ days after last dose ≤ 24
28	Off Treatment Day 28 b	28	25 ≤ days after last dose ≤ 31
35	Off Treatment Day 35 b	35	32 ≤ days after last dose ≤ 38

a Last day of on-treatment for patients permanently discontinuing study drug prior or on to Week 12. Assessments that occur on the date of last dose or less than 2 days after last dose are considered on treatment and summarized using Table 3 windows.

b The off-treatment values indicate the value closest to the date of last dose.

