### **8.1.1.3. Off-Treatment MMRM eGFR Analysis for Week 12 and Week 17 Completers**

Analyses will be conducted as described in Section 8.1.1 for patients who have completed 12 weeks of treatment and have off-treatment eGFR values collected within each of the analysis visit windows through Week 17 (Table 4).

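### Completers' final visit has two target days, 1 to 4 days apart; a Week 17 draw after a Day 81 Week 12 visit falls one day outside the SAP's last off-treatment window

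*Protocol*

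**What the plan says.** Three rules bear on the date of a completer's last visit.

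- **From randomization.** Protocol 7.1: "All patients, including patients who discontinue treatment early, should complete the end-of-study (EOS) visit 17 weeks after randomization". The same rule stands in the protocol synopsis, the SAP's opening summary and SAP 3.1.
- **From the last dose.** Protocol 7.1: "The OT day corresponds to days after last dose. Day 1 OT is the first day after receiving the last dose". The heading over the off-treatment columns of the protocol's Table 4 uses the same anchor.
- **From the end-of-treatment visit.** Protocol 7.6.5: "All visits in the OT Period should be scheduled based on the date of the Week 12/EOT visit".

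For completers these rules govern a single visit. The title of Protocol 7.6.6 equates the end-of-study visit with OT Day 35, and SAP Table 2 heads the column "OT Day 35 –3 Week 17". Only footnote a to the schedule separates the two, and only for patients who stop drug early: "there will be both an OT Day 35 visit scheduled 35 days following the last dose of IP and an EOS visit". No sentence says which anchor governs for completers.

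On the Week 12 visit, Protocol 7.6.4 says: "Careful attention should be paid to ensure the visit is scheduled between Day 81 and Day 84". It places the last dose on the day before. On the analysis side, the OT Day 35 window in SAP Table 4 is "32 ≤ days after last dose ≤ 38", and no later window follows. The completer analyses in SAP 8.1.1.3 and 8.1.1.4 take only patients who "have off-treatment eGFR values collected within each of the analysis visit windows through Week 17".

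**The concern.** A visit defined by days since the last dose and also by weeks since randomization has one date only if the last dose falls on a fixed study day. Here it can fall on any of four days, all before Day 84. A site can therefore follow the 17-week sentence, hold Week 12 on a permitted day, and still draw the final sample outside the window in which the SAP would use it.

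Such a value has nowhere else to go. It is too late for the OT Day 35 window, and SAP Table 3 excludes it from the on-treatment visits. The patient then has no Day 35 observation in the off-treatment MMRM (SAP 8.1.1) or the observed-case ANCOVA (8.1.1.1). Because the completer analyses need a value in every window, the patient drops out of both altogether. Day 35 is the last point of the period that Protocol section 5 uses to judge the drug's effect on irreversible loss of kidney function.

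**Working it through.** **Inputs**

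- Week 12 visit on study day w = 81, 82, 83 or 84; last dose on day w − 1 (Protocol 7.6.4).
- OT day = days after last dose (Protocol 7.1). SAP 5.5.1 computes it as visit date minus last-dose date.
- Week 17: the schedule numbers Week 12 as Day 84, so Week 17 = 17 × 7 = Day 119. SAP 5.5.1 makes the randomization date Day 1, so exactly 17 weeks later is 119 + 1 = Day 120. I carry both readings.
- SAP Table 4 window for OT Day 35: 32 to 38 days after last dose.

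**The plan's own equation, OT Day 35 = Week 17**

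It holds only if the 35 days run from a Week 12 visit on Day 84: 84 + 35 = 119. Counted from the last dose, even a Day 84 visit gives 83 + 35 = 118.

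**Dates by Week 12 visit day**

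OT Day 35 target = (w − 1) + 35. Days after last dose at Week 17 = 119 − (w − 1), or 120 − (w − 1).

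| Week 12 visit | Last dose | OT Day 35 target | Gap to Day 119 | Days after last dose, Day 119 draw | Days after last dose, Day 120 draw |
|---|---|---|---|---|---|
| Day 81 | Day 80 | Day 115 | 4 | **39** | **40** |
| Day 82 | Day 81 | Day 116 | 3 | 38 | **39** |
| Day 83 | Day 82 | Day 117 | 2 | 37 | 38 |
| Day 84 | Day 83 | Day 118 | 1 | 36 | 37 |

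Bold entries exceed the limit of 38. On the Day 119 reading, one of the four permitted Week 12 days fails, by one day. On the Day 120 reading two fail, by two days and one day.

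**If a minus-3 tolerance is allowed on Week 17**

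Draws on Days 116 to 119 are 36–39, 35–38, 34–37 and 33–36 days after last dose for w = 81, 82, 83 and 84. Only 1 of the 16 combinations is outside the SAP window: w = 81 with a Day 119 draw. On the Day 120 reading (Days 117 to 120) the ranges are 37–40, 36–39, 35–38 and 34–37, and 2 + 1 = 3 of 16 are outside.

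**The other two anchors**

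- Counting 35 days from the last dose puts the draw at 35 days in every case, and at 32 to 38 days even with 3 days either side. It is always in the window.
- Counting 35 days from the Week 12 visit puts it at w + 35 − (w − 1) = 36 days in every case. It is always in the window.

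**The case against.** The strongest reply is that most of the text already sends sites to the right date. The schedule heading, the OT-day definition and the title of 7.6.6 all point to the last dose, and 7.6.5 points to the end-of-treatment visit, which is equally safe. The 17-week sentence says should, and footnote a, written for early stoppers, says approximately. Protocol 7.6.3 also tells sites to watch visit windows from Week 12 onward, and a 39-day draw is late against the OT Day 35 column itself. The loss is thin too: the patient stays in the off-treatment MMRM through the other five off-treatment visits, and the imputation ANCOVA in SAP 8.1.1.2 covers a missing Day 35.

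All of that stands, and it limits the point to a corner case. It does not remove the point. The 17-week sentence expressly covers all patients, nothing ranks it below the other anchors, and a site acting on it after a Day 81 visit has broken no rule in that sentence or in 7.6.4.

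A reader might infer three stronger things that the documents do not support:

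- **That completers must meet two incompatible dates.** The wording is should. After a Day 81 visit, draws on Days 116 to 118 are 36 to 38 days after last dose and are analysed.
- **That 7.6.5 misdates the whole off-treatment series.** Read with 7.1, it gives the same calendar for OT Days 3 to 28, and counting 35 days from that visit keeps the final draw in the window.
- **That the schedules disagree on tolerance.** SAP Table 2 shows minus 3 for the final visit, while the protocol's Table 4 appears to show 3 days either side. This may be only a table-conversion effect. I do not count it as an error or rest the conclusion on it.

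**Conclusion.** The point holds as a minor wording conflict with a small, avoidable analysis consequence. For completers the two target days differ by 1 to 4 days (2 to 5 on the Day 120 reading). A draw on the Week 17 target day misses the last SAP window by one day after a Day 81 Week 12 visit. On the Day 120 reading it misses by two days after a Day 81 visit and by one day after a Day 82 visit.

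This assumes that the last dose is the day before the Week 12 visit, as instructed, and that the site schedules the final visit from randomization. The documents do not say how many patients had Week 12 on Day 81 or 82, or which anchor sites used, so the number of affected patients cannot be estimated and may be zero.

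What is exposed is the last time point of an exploratory endpoint and two supplementary completer analyses. The Week 12 primary endpoint, the secondary endpoint by etiology and the sample size are not touched.

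**What to change.** 1. **Name one anchor.** In every copy of the 17-week sentence (protocol synopsis and 7.1; SAP summary and 3.1), state that for completers the end-of-study visit is OT Day 35 counted from the last dose, and that the 17-week date applies to patients who discontinue drug early. All four copies need the change, or they will contradict one another. Protocol 7.6.5 need not be rewritten.
2. **Protect draws already taken.** In SAP Table 4, raise the upper limit of the OT Day 35 window from 38 to at least 40 days, before unblinding. Forty days covers a target-day draw on either reading of Week 17. Keep the closest-to-target rule in SAP 5.5.3, so that a value nearer Day 35 still takes precedence.

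The cost is low. No visit or procedure is added. The protocol wording needs an amendment under Protocol 15.5 and helps only visits not yet held. The SAP change is one table cell, with a slightly wider last window as its only drawback. SAP version 2 is dated 06-OCT-2021, and the protocol estimated last patient completion in July 2021. If follow-up has ended, the SAP cell is the part that still matters.
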